#### 10.6.3 Lost to follow-up (LTFU) rate

Since the LTFU rate in potential complete responders would affect the primary endpoint (see [Section 10.7](#)), the LTFU rate for each arm will be closely monitored by the study team. After 50% of the ITT population has completed assessment for the primary endpoint, a report will be sent to the DSMB documenting the LTFU rate by arm, as well as the response at any visit(s). When assessing this rate, all participants not providing evaluable endpoint data will be included. Consideration will be given to halting the study if the absolute LTFU rates differ by at least 15%, since a significant arm difference in the CR rate could be an artifact of differential LTFU rates.

### 10.7 Primary Analyses

The primary analysis population for efficacy and safety is an intent-to-treat (ITT) population, which consists of all participants who are randomized to 5-fluorouracil 5% or observation. The proportion of participants achieving complete response in the 5-fluorouracil 5%, and the proportion of participants with spontaneous regression in the observation arm will be calculated as the number achieving complete response or experiencing spontaneous regression through the primary endpoint visit (Week 20) divided by the number in the intent-to-treat population. For the treatment comparison (topical 5-

fluorouracil 5% vs. observation) the proportions will be compared across sites using stratified Mantel-Haenszel-Cochran tests at the one-sided 0.05 alpha level. This means that participants who drop out or do not provide evaluable data contribute to the analysis since they are included in the denominator, i.e., they are essentially treated as failures.

Since the imiquimod arm was stopped early, we will describe comparisons between imiquimod and observation using only the participants randomized to imiquimod and observation prior to closure of the imiquimod arm. As a secondary objective, imiquimod 2.5% and topical 5-fluorouracil 5% will be compared using a stratified Mantel-Haenszel-Cochran test at the two-sided 0.05 alpha level using participants randomized prior to the closure of the imiquimod arm.

The primary endpoint will include intra-anal HSIL present on cytology or histology. Perianal HSIL will be descriptively reported separately, as well as combined with the primary endpoint. In addition to the primary intent-to-treat analysis (which includes all randomized participants), we will perform a sensitivity analysis that treats participants who receive HSIL treatment other than randomized treatment (or observation participants that receive any treatment) prior to Week 20 as failures; participants who are lost to follow-up or inevaluable are also still treated as failures. We will also perform a per-protocol analysis using the subset of participants who were adherent to the protocol.

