### **10.3 Sample Size Estimation**

The original sample size was based on the assumption that treatment of anal HSIL lesion with topical therapy (topical 5-fluorouracil 5%) will have a minimum CR rate of 40% as compared to a maximum regression rate of 10% in the observation arm. Due to the slow accrual rate, the sample size was reduced, and the revised sample size was decided by the expected accrual close date (01 July 2023). Thirty five participants per arm (or 70 in total for observation and 5FU arms) would be the revised sample size. Eighteen participants were accrued to the imiquimod arm prior to this arm being closed because of lack of drug availability. The comparison of imiquimod to observation is no longer sufficiently powered to test efficacy; comparisons to imiquimod will be considered exploratory.

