#### 10.6.2 Futility and efficacy halting rules

An interim analysis is planned after 50% of the ITT population has completed assessment for the primary endpoint to assess the futility of achieving a significant result if the study continues and to potentially demonstrate efficacy before all participants are enrolled. For the comparing topical 5-fluorouracil 5% vs observation, group sequential methods will be used to compare efficacy endpoints preserving the overall one-sided significance level of 0.025 for each comparison. To assess superiority of a treatment arm in comparison to observation the Lan-DeMets stopping boundaries will be used. To assess futility, the O'Brien-Fleming futility boundaries will be used. The interim analyses will be reviewed by the AMC Data and Safety Monitoring Board (DSMB) by the 50% point.

**Table 10-A: Statistical test boundaries and associated operating characteristics for testing efficacy of 5-fluorouracil 5% vs. observation**

Analysis	Total Number (%) of Subjects*	$H_0$ (Futility) Bound Z (P-value)	$H_1$ (Efficacy) Bound Z (P-value)	Overall $\alpha$ Spent	Overall $\beta$ (1-power) Spent
1 (Interim)	35 (50%)	0.258 (0.398)	2.963 (0.002)	0.002	0.020
2 (Final)	70 (100%)	1.955 (0.025)	1.955 (0.025)	0.025	0.100

\*Total number of subjects equals the number in 5FU arm plus observation arm.

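### Section 10.7 tests the primary comparison at one-sided 0.05, while Section 10.6.2 and Table 10-A are built to one-sided 0.025; following Section 10.7 roughly doubles the stated type I error.

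*Combined protocol and SAP*

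**What the plan says.** Section 10.7 (Primary Analyses) defines the primary test. For 5FU versus observation, on Week 20 response in the intent-to-treat population, "the proportions will be compared across sites using stratified Mantel-Haenszel-Cochran tests at the one-sided 0.05 alpha level". The section refers neither to the interim analysis nor to any group-sequential boundary.

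Section 10.6.2 (Futility and efficacy halting rules) covers the same comparison and says that "group sequential methods will be used to compare efficacy endpoints preserving the overall one-sided significance level of 0.025 for each comparison". It plans one interim look: "An interim analysis is planned after 50% of the ITT population has completed assessment for the primary endpoint". On the boundaries it says "To assess superiority of a treatment arm in comparison to observation the Lan-DeMets stopping boundaries will be used" and "To assess futility, the O'Brien-Fleming futility boundaries will be used". Table 10-A, titled for 5FU versus observation, gives:

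| Analysis | Subjects | Futility Z | Efficacy Z | Cumulative alpha | Cumulative beta |
|---|---|---|---|---|---|
| Interim | 35 (50%) | 0.258 | 2.963 | 0.002 | 0.020 |
| Final | 70 (100%) | 1.955 | 1.955 | 0.025 | 0.100 |

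**The concern.** Both sections prescribe the final test of the same hypothesis on the same endpoint, and they give different critical values: about 1.645 under Section 10.7 and 1.955 under Table 10-A. Any final statistic between the two is a success by one section and a failure by the other. An analyst who follows Section 10.7, the natural place to look for the primary test, would exceed the error rate that Section 10.6.2 says is preserved.

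Timing makes this more pressing. Section 1.2 records that enrollment closed on 01 July 2023, and version 8.0 is dated 02 August 2023. If the threshold is left open until the outcomes are known, the choice between the two rules could be made, or could appear to have been made, after seeing the result.

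**Working it through.** **Inputs.** From Section 10.6.2 and Table 10-A: one-sided alpha 0.025, interim at 50% information, bounds 2.963 / 0.258 / 1.955, beta 0.100. From Section 10.7: one-sided 0.05, i.e. Z = 1.645. From Section 10.3: 35 per arm. Z1 and Z2 are the interim and final statistics, treated as bivariate normal with correlation √0.5 = 0.707. Site stratification is ignored.

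**Step 1: reproduce Table 10-A.** The plan does not name the Lan-DeMets spending function, so the O'Brien-Fleming type was assumed:

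α(t) = 2[1 − Φ(z_{α/2}/√t)]

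With α = 0.025 and t = 0.5, this spends 0.00153 at the interim, giving Z = 2.963. The same form for beta = 0.10 spends 0.0200, giving a futility bound of 0.258. Solving for the final bound with futility treated as binding gives 1.955. All three bounds match the table.

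Two alternatives do not match:

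- 0.025 with non-binding futility gives a final bound of 1.969.
- One-sided 0.05 with binding futility gives 2.538 / 0.038 / 1.648.

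The table is therefore a one-sided 0.025 design with binding futility.

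**Step 2: type I error under each final threshold c.** With futility obeyed,

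P(Z1 > 2.963) + P(0.258 < Z1 < 2.963, Z2 > c)

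With futility not obeyed, the lower limit 0.258 is removed.

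| Final threshold | Futility obeyed | Futility not obeyed |
|---|---|---|
| 1.955 (Table 10-A) | 0.0250 | 0.0258 |
| 1.645 (Section 10.7) | 0.0476 | 0.0503 |

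Relative to the stated 0.025, Section 10.7 gives 0.0476/0.025 = 1.9 times to 0.0503/0.025 = 2.0 times the error.

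**Step 3: results on which the two sections disagree.** Take 9/35 versus 3/35 responders (26% versus 9%). The pooled proportion is 12/70 = 0.1714 and the difference is 6/35 = 0.1714.

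SE = √(2 × 0.1714 × 0.8286 / 35) = 0.0901

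Z = 0.1714/0.0901 = 1.90

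This passes 1.645 and fails 1.955. So do 3 v 0, 5 v 1, 7 v 2, 10 v 4, 11 v 5 and 12 v 5.

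Ignoring interim stopping, the probability that the final unstratified Z falls in this zone is about 6% at the Section 10.3 rates of 40% and 10%. It is about 12% at 30% versus 10% (an assumed, weaker effect).

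**The case against.** Four points can be made on the other side.

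- **Table 10-A can be read as the governing rule.** It is specific to 5FU versus observation, has an explicit final row, and was revised for version 8.0. The 0.05 in Section 10.7 could then be leftover wording. But no text gives the table precedence, and Section 1.2 says the primary analysis is unchanged, so a correction is still needed.
- **The documents do not prove that 0.025 was intended.** At 35 per arm and 40% versus 10%, a fixed design has power of about 0.84 at one-sided 0.025 and 0.91 at one-sided 0.05; the second is nearer to the 0.90 that Table 10-A implies. This is only suggestive, because Section 10.3 ties those rates to the original sample size. If 0.05 was intended, Section 10.6.2 and all of Table 10-A would have to be recomputed, so one section must change either way.
- **The factor is not exactly two under the table's own design.** It is 1.9 if binding futility is respected and 2.0 otherwise. This is correct, and both figures are given above.
- **A fixed 1.955 holds the error at 0.025 only if the interim fell at 50% of 70 and futility is binding.** This stands as a refinement. As an illustration, suppose the interim was at 50 of 70 (half of the former 100) and futility is non-binding. The final bound would then be about 2.00, and using 1.955 would give an error of 0.0275. The documents do not say when, or whether, the interim took place.

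Two other possible defences do not help. The phrase in "preserving the overall one-sided significance level of 0.025 for each comparison" may date from a design with two treatment arms, but Section 10.7 applies the full 0.05 to the single remaining primary comparison. Nor is 0.05 evidently a two-sided figure, since the same section uses a two-sided 0.05 for imiquimod versus 5FU and so distinguishes the two.

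**Conclusion.** The concern holds. Sections 10.7 and 10.6.2 give incompatible thresholds for the primary test. Applying Section 10.7 at the final analysis raises the overall one-sided type I error from 2.5% to between 4.8% and 5.0%. Section 10.6.2 and every bound in Table 10-A agree on 0.025; Section 10.7 stands alone. The type I error figures rest on the normal approximation, one interim at exactly 50% information, and no allowance for site stratification; the responder counts are illustrative for that last reason. This must be fixed, because it concerns the decision rule for the primary endpoint.

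**What to change.** In Section 10.7, replace the one-sided 0.05 level for 5FU versus observation with wording to this effect: the overall one-sided significance level is 0.025; at the final analysis, efficacy is declared only if the stratified Mantel-Haenszel-Cochran statistic reaches the final group-sequential boundary of Section 10.6.2, which is Z = 1.955 if the interim took place at 50% information as planned. If the interim was at another fraction, or the futility bound is not treated as binding, the final boundary should be recomputed from the same spending function. That function should be named, and the plan should say whether futility is binding. A two-sided 95% confidence interval for the difference should be reported; it corresponds closely, though not exactly, to a 1.955 boundary after an interim look.

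If the sponsor did intend one-sided 0.05, Section 10.6.2 and Table 10-A must be recomputed and the higher error rate stated openly.

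The recommended change costs one sentence in Section 10.7, plus the short clarification of the boundary. It needs no new data or participants. The threshold becomes stricter than Section 10.7 now states, but it is the one already in the monitoring plan. The amendment should be dated before any comparison of outcomes by arm outside the DSMB.

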## **SITES PARTICIPATING IN THE STUDY**

This protocol will be open to all interested AMC sites approved by the HPV Working Group. The approval will be based on the certification to perform high resolution anoscopy (HRA).

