## **10.0 STATISTICAL CONSIDERATIONS**

### **10.1 Rate of Accrual**

This study is expected to accrue eight participants per month for a total of 118 participants (50 per arm for observation and 5FU arms and 18 to the imiquimod arm, which closed because of lack of drug availability). However, the rate of accrual has been approximately one participant per month from 2021-2023. With Version 8.0, the sample size has been reduced to 88 participants (35 per arm for observation and 5FU arms and 18 to the imiquimod arm).

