### **10.2 Randomization**

The study will use a stratified, random permuted block randomization scheme with strata being sites. This approach ensures that arms are balanced within sites.

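### The primary test makes every site a stratum with about 70 participants and no rule for sparse sites; depending on the unstated number of sites, this costs about 0 to 6 points of power that pooling small sites would mostly recover

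*Combined protocol and SAP*

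**What the plan says.** Section 10.2 randomises by a "stratified, random permuted block randomization scheme with strata being sites" and adds: "This approach ensures that arms are balanced within sites". Block size is not given.

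Section 10.7 analyses along the same lines: "the proportions will be compared across sites using stratified Mantel-Haenszel-Cochran tests". It says nothing about sites with few participants or with only one of the two arms.

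On size, section 10.3 states: "Thirty five participants per arm (or 70 in total for observation and 5FU arms) would be the revised sample size". The planning rates, given for the original sample size, are a "minimum CR rate of 40% as compared to a maximum regression rate of 10% in the observation arm".

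The number of sites is not stated. The page on participating sites says: "This protocol will be open to all interested AMC sites approved by the HPV Working Group". Section 10.1 reports that "the rate of accrual has been approximately one participant per month from 2021-2023". The imiquimod arm closed at version 5.0, so the scheme went from three arms to two during accrual.

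**The concern.** Permuted blocks balance the arms within a site only when its blocks are filled. If 70 participants are spread over many sites, some sites will stop partway through a block, and the move from three arms to two adds another break. A site left with one arm gives the stratified test no information, and an unbalanced or very small site gives less than its share.

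What is at stake is power. The two arms were cut from 100 participants to 70, so there is little to spare. A second risk is procedural: if sparse sites are first noticed at analysis, the choice of how to combine them may be made with outcomes in view.

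**Working it through.** **Why a one-arm site drops out.** For site k, let n1 and n0 be the numbers on 5FU and observation, N = n1 + n0, m the responders and a the responders on 5FU. The test sums over sites

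- numerator: a − n1·m/N
- variance: n1·n0·m·(N − m) / [N²(N − 1)]

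If n0 = 0, then a = m and n1 = N, so both terms are zero. The same holds if n1 = 0. A site with one participant also adds nothing.

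**Why small or unbalanced sites are inefficient.** With a common response rate p, the expected null variance is p(1 − p)·n1·n0/N, so n1·n0/N measures a site's information. Four participants split 2:2 give 1.0, split 3:1 give 0.75, and split 4:0 give 0. Very small strata lose something even when balanced. At 40% v 10%, a 1:1 site has m = 1 with probability 0.4×0.9 + 0.6×0.1 = 0.42, so its expected variance is 0.42/4 = 0.105. The same pair in one large stratum has 0.5×0.25×0.75 = 0.094. The signal (0.5×0.30 = 0.15) is the same, and the variance is 12% larger.

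**The plan's own power figure.** Table 10-A in section 10.6.2 gives overall beta 0.100 at 70 participants. Its bounds reproduce (alpha 0.0250; beta 0.020 at the interim and 0.100 overall) at a drift of 3.268. Fixed-sample power for 35 per arm at one-sided 0.025 is:

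- pooled variance: (0.30 − 1.96×√(2×0.25×0.75/35)) / √((0.24 + 0.09)/35) = (0.30 − 0.203)/0.0971 = 1.00, or 84.1%
- unpooled variance: 0.30/0.0971 − 1.96 = 1.13, or 87.1%

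With the Table 10-A bounds, group-sequential power is 82.0% (pooled) to 86.6% (unpooled). So 90% is not reproduced even before any loss from stratification. That is a separate matter, but it shows there is no reserve.

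**Simulated power, equal response rates across sites.** Inputs from the protocol: N = 70, 40% v 10%, permuted blocks within site. Assumed: 5 to 20 sites, equal or skewed in size, and block size. One-sided 0.025, final test only. Each cell is power (%) with every site a stratum / with sites under six participants pooled (difference in points).

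| Sites | Blocks of 2, equal | Blocks of 2, skewed | Blocks of 6, equal | Blocks of 6, skewed |
|---|---|---|---|---|
| 8 | 85.1 / 85.2 (0.1) | 85.4 / 85.6 (0.2) | 84.6 / 84.7 (0.1) | 85.2 / 86.0 (0.8) |
| 10 | 84.8 / 84.9 (0.1) | 84.5 / 85.6 (1.1) | 84.1 / 84.8 (0.7) | 84.1 / 85.6 (1.5) |
| 15 | 84.5 / 85.1 (0.6) | 83.9 / 85.5 (1.6) | 82.1 / 85.1 (3.0) | 81.5 / 85.5 (4.0) |
| 20 | 83.5 / 86.0 (2.5) | 82.9 / 85.9 (3.0) | 79.4 / 85.5 (6.1) | 79.0 / 85.1 (6.1) |

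At 5 sites (blocks of 4) the loss is about 0. A scheme closer to the trial's history (54 participants in three-arm blocks of 6, then 34 in two-arm blocks of 4, unequal sites, bound 1.955) gives 84.4/85.3 at 8 sites, 83.1/85.4 at 12, 82.0/85.3 at 16 and 80.8/85.2 at 20: differences of 0.9, 2.3, 3.3 and 4.4 points.

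With blocks of 4, the expected number of participants carrying no weight is 0 at 5 sites, 0 to 0.7 at 8, 0.2 to 1.6 at 10, 1.6 to 4.4 at 15 and 4.5 to 7.2 at 20.

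**Simulated power, response rates differing between sites** (log-odds SD 1, an assumption; blocks of 4).

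| Sites | Equal sizes | Skewed sizes |
|---|---|---|
| 8 | 82.6 / 82.5 (−0.1) | 81.6 / 81.6 (0.0) |
| 10 | 81.5 / 81.3 (−0.2) | 81.3 / 81.7 (0.4) |
| 15 | 80.9 / 80.7 (−0.2) | 79.8 / 81.8 (2.0) |
| 20 | 78.1 / 79.1 (1.0) | 76.9 / 80.2 (3.3) |

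A second set of runs at the same SD put the gain at 20 skewed sites at 81.1 − 76.8 = 4.3 points. It also found the largest cost of pooling: 0.6 point at 12 equal-sized sites and 0.8 point at 15.

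**Other checks.** With the Table 10-A interim look, the loss against an unstratified test is 0 to 0.8 point at 5 to 8 sites and 5.4 to 5.5 at 20; pooling leaves 0.4 or less. At the one-sided 0.05 level that 10.7 names, with blocks of 4, the loss is 0 to 0.6 point at 5 to 8 sites and 2.9 to 3.7 at 20. Type I error in final-test runs was 0.023 to 0.027 against 0.025, and 0.022 to 0.029 with pooling. Simulation error is about 0.4 to 0.6 point per power estimate.

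**The case against.** The test matches the randomisation strata, which is a conventional and valid choice. The protocol gives no site count, and the accrual rate in 10.1 covers only 2021-2023 and all sites together, so it does not show that many sites are sparse. With few, large sites almost nothing is lost. This stands, and it is why the loss can be given only as a range that starts at zero.

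Site differences are plausible: cytology is read locally (Appendix III) and each site's own anoscopist takes the biopsies (Appendix V). Stratification then helps. At SD 1 and 8 sites it gains 2.5 to 3.7 points over an unstratified test. This also stands, and it rules out a reading that a reader might be tempted by, that site stratification should be dropped. Pooling only the small sites keeps that gain.

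A reader might also infer that the test contradicts the intent-to-treat analysis, because some randomised participants carry no weight. The documents do not support that. Section 10.7 defines intent-to-treat by population and denominator, and everyone randomised to the two arms still counts in the reported proportions. Zero weight in an uninformative stratum is an efficiency loss, not an exclusion.

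Finally, pooling needs care. With unequal sites, the pooled stratum itself held one arm in about 15% of simulated trials at 5 sites and 6% at 8. More sites also fall below a cut-off at 35 participants than at 70. Both points stand and are met in the fix.

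**Conclusion.** The point holds as an efficiency concern with a cheap remedy. Every site is a stratum, there is no rule for sparse sites, and a one-arm site contributes nothing to the test. Against pooling small sites, the power lost is about 0 to 1 point at 5 to 8 sites, about 0 to 4 at 10 to 16, and up to about 6 at 20. With strong differences between sites (log-odds SD 1) it is about 0 to 4 points.

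These figures rest on assumed site numbers, site sizes and block sizes, and on 40% v 10%. A flat statement that several points are lost would go beyond the documents. Validity is not in question. The wording in 10.2 that blocks ensure balance within sites is too strong, but correcting it would change only the text.

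Two neighbouring issues are larger and separate: 10.7 tests at one-sided 0.05 while 10.6.2 speaks of "preserving the overall one-sided significance level of 0.025 for each comparison", and the 90% power in Table 10-A is not reproduced at 70 participants.

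**What to change.** Add to 10.7, using site and arm counts only and before anyone choosing the rule has seen outcomes by arm:

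- Sites with fewer than six participants in the 5FU and observation arms combined, or with only one of these arms, are pooled into one stratum.
- If that stratum still holds only one arm, it is merged with the next smallest site.
- The same rule is applied to the data available at each analysis, interim and final.
- The fully site-stratified test is reported as a sensitivity analysis.

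Enrolment has closed (section 1.2), so the counts can be tabulated now; if sites are few and large, the rule changes almost nothing. The text is short, but an amendment needs CTEP and IRB approval (section 11.2). The trial is open-label, the protocol statistician is a non-voting DSMB member (Appendix VIII), and the documents do not say whether the interim has taken place. The amendment should therefore record who set the rule and what they had seen.

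The statistical cost is that differences among the pooled small sites are not controlled. In the scenarios run this cost at most about 0.8 point of power, with equal-sized sites and strong heterogeneity.

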## 10.8 Secondary Analyses

To examine the tolerability and safety of the three arms, descriptive statistics for AEs will be computed. AEs will be summarized at the event level and subject level according to severity. AEs will be stratified according to those reported at or before Week 20 and after Week 20 since those in the observation arm have to option of being randomized to imiquimod or 5FU at Week 20. Proportions and their exact binomial 95% confidence intervals will be calculated. We will compute summary statistics for the amount of study drug taken by measuring the mass of study drug dispensed (weight of study drug container at baseline – weight of study drug at the end of treatment).

Similarly, we will assess for PR in two ways. We will compare between arms the number of quadrants with HSIL found on biopsies treating the response as an ordinal variable. The biopsy plan for Week 20 and 48 (see [Appendix V](#)) specifies that at least one biopsy be obtained from each quadrant. Biopsies used for eligibility will generally be obtained through routine care and will not necessarily have four quadrant biopsies, so we are not able to look at the within participant change in the number of quadrants with HSIL on biopsy. Therefore, this comparison between arms assumes that the extent of disease at enrollment is balanced between arms, which is reasonable given randomization. We will also compare the proportion of participants achieving CR or PR (as per [Section 9](#)) with imiquimod or 5FU as compared to observation only using similar approaches as the primary objective.

We will evaluate the effect of imiquimod and 5FU on persistence of HPV type specific infections. We will report the frequency and proportion of HPV types present at baseline that are no longer detected at Week 20. We will also report the frequency and proportion of new HPV infections detected at Week 20 that were not present at baseline. Proportions and their exact binomial 95% confidence intervals will be calculated.

HSIL outcomes at Week 44 will be analyzed similarly to those at Week 20. Results for the observation arm will be stratified into cross-over treatment groups.

To evaluate the relationship between smoking and sexual behaviors on treatment efficacy, tolerability, and HPV, regression models will be fit for each treatment arm. For treatment efficacy, a logistic regression model will be fit; for endpoints that are available over time, a generalized estimating equations (GEE) model may be fit. A model that incorporates treatment arm will be developed to assess the role of treatment on these endpoints in the presence of behavioral covariates.

